6.0 Data and Specimen Banking NA

7.0 Sharing of Results with Participants

PROTOCOL TITLE: Does Social Buffering Continue to be Effective Over the Peripubertal Period
When Friends Share the Stressor Experience?

VERSION DATE: v.3.3 3.31.23

7.1

7.2

7.3 Results will only be shared with participants in aggregate. Regarding other biologic measures we take, abnormal values are commonly due to an interfering substance present in the sample (ex, milk for salivary cortisol). Without a body of evidence, it seems unethical to alarm families given an out-of-range assay value and therefore we do not plan to share individual results with participant.

8.0 Study Population

8.1 Inclusion Criteria: Healthy 11-14 year olds. Additional inclusion criteria are imposed in ensure that youth will be able to follow the study procedures, sufficient vision, hearing, and language skills to provide verbal and written assent, see and read stimuli presented on the computer screen, and hear verbal instructions provided by the experimenter and judges.

8.2 Exclusion Criteria: Premature birth (less than 37 weeks), congenital and/or chromosomal disorders (e.g. cerebral palsy, FAS, mental retardation, Turner Syndrome, Down Syndrome, Fragile X), Autism Spectrum Disorders, history of serious medical illness (e.g., cancer, organ transplant), serious psychiatric illness, or youth taking systemic glucocorticoids or beta-adrenergic medications.

8.3 Screening: Screening will occur by asking parents questions at the time of recruitment. To reduce confounding age and pubertal stage, we will use a stratified recruitment method. During recruitment, parents will be asked 3 questions about their child's physical development, and children will be initially categorized into Pre/Early and Mid/Late Puberty. As cells fill, participants will no longer be enrolled into those cells. Also, to increase minority representation we will also sample across zip codes with higher racial and ethnic minority representation.

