which youth is the target and this is the youth we select to balance pubertal stage and age, while in the close friend conditions, the close friend only needs to be within two years the age of the target youth; (2) in the “Close Friend Gives Support” condition, the friend will not be assessed and will only be there for moral support and to provide information on his/her friendship with the target youth. The collected data from the non-target youth will be analyzed using non-sponsored funds available to the PIs and co-regulation analyses may be conducted.

Note: These sessions will be recorded, as part of the challenge, to document the session, and to make behavioral response to the task available for later coding.

Pubertal Development: All youth will also complete the Morris and Udry (1980) pubertal development questionnaire, which allows placement in Tanner stages for hair, testicles, and breast development. **Questionnaires.**

Demographic Questionnaire: Parents will complete information on pre-tax family income, education level of parent(s), composition of the household, and medications that the child regularly takes.

Daily Diary: The parent and the youth both will report the following for the child that day: the time of wake up, estimated duration of sleep, medication usage, illness/fever, physical activity, and caffeine consumption.

Relationship Quality: Participants will complete the Network of Relationships Inventory - Behavioral Systems Version (NRI-BSV, Furman & Buhrmester, 2009) for the parent who accompanies them and their close friend. This questionnaire is based on an integration of attachment and Sullivanian theory and assesses three systems that are expected to be key in close relationships: attachment, caregiving and affiliation. The scales are: companionship, seek safe haven, seek secure base, provide safe haven, provide secure base, conflict, antagonism and criticism. We will also add 3 scales from the NRI-Relationship Qualities Version: Emotional Support, Approval and Satisfaction. Each scale consists of 3 items scored on a 5-point Likert scale. Psychometric qualities are high. Condition differences in quality of relationships will be examined and included as covariates if groups differ significantly. Otherwise, in follow-up analyses we will examine whether social buffering effects are stronger in relationships the child views as more supportive.

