14.0 Statistical Considerations

14.1 Data Analysis Plan: 200 primary participants, including 100 females and 100 males. Within each group there will be 50 early and 50 late puberty participants.

Study Design. This randomized control study will assign study participants into one of four conditions: Close friend both tested, Unfamiliar Peer both tested, Received support from close friend who is not tested, and no partner. To perform the randomization, participants will first be placed into one of four groups based on sex and pubertal stage: early puberty, female;

PROTOCOL TITLE: Does Social Buffering Continue to be Effective Over the Peripubertal Period
When Friends Share the Stressor Experience?

VERSION DATE: v.3.3 3.31.23

late puberty, female; early puberty, male; and late puberty, male. Next, participants within a group will be randomly assigned to one of four conditions equally in order to have a balanced design. Pubertal stage will then be treated as a continuous variable.

Statistical Methods

Preliminary Analyses to Determine Covariates Need for Primary Analyses. The purpose of collecting data on potential covariates is to identify variables that are correlated with both the independent variable (social buffering condition, sex, pubertal stage) and the primary outcome measures. Those covariates that are associated with the independent and outcome variables will be controlled for in the primary analyses. Those that are not will be used to describe the sample, but will not need to be included in the analyses to obtain unbiased estimates. For each potential covariate (listed as “other type” in section 4.3, Outcome Variables), we will conduct correlations or t-tests with pubertal stage, and t-tests, ANOVAs, or chi-square tests (as appropriate) with sex and condition. If data do not confirm to modeling assumptions, we will use non-parametric analogs instead.

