14.2 Power Analysis: For the power analysis for the primary analyses, we calculated the minimum detectable effect size (MDES) assuming $n = 200$, $\alpha = .05$, and power = .80 with a conservative estimate of 12 covariates in our model (see section 4.3). Power was calculated in R (R Core Team, 2018) using the pwr library (Champely, 2018). A power analysis was performed to quantify the MDES (measured as f^2) for a three-way interaction between the social buffering condition, sex, and pubertal stage within a multiple regression model controlling for all potential covariates, two-way interactions, and main effects (the most complex model considered in our primary analysis, see equation 1 below). Assuming these conditions, we should be able to detect an f^2 of 0.056. In other words, adding the three-way interaction to a model containing the covariates and all lower order interactions and main effects, the three-way interaction would need to explain an additional 5.6% of the variability to be detected. This falls between Cohen’s criteria for a small ($f^2 = .02$) and medium-sized effect ($f^2 = .15$) (Cohen, 1988). With a sample size of 200, even if we lost 40 of the participants, assuming all the previous conditions except a sample size of 160, we would still be power enough to detect an f^2 of .070, or still within a small-medium effect size. As the number of covariates decreases, the size of the MDES will decrease. Therefore, this represents a conservative estimate of power for our primary analyses as we are likely to have fewer covariates in our models and will use multiple imputation to correct for missing data. For the two-way interaction and main effects models, described below, the power will be larger than these reported values as the

PROTOCOL TITLE: Does Social Buffering Continue to be Effective Over the Peripubertal Period
When Friends Share the Stressor Experience?

VERSION DATE: v.3.3 3.31.23

models will be simpler. In addition, we ran a power analysis that corrected for multiple comparisons using the conservative Bonferroni's adjustment. Because we expect to run 9 independent multiple regression models or fewer, we ran our models assuming an alpha of 0.05 / 9. Based on this reduced alpha, we expect to be able to detect an effect of .07.

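### No condition-by-age term is described, so moderation credited to pubertal stage could partly reflect age: a small effect if age is well balanced, a material one if it is not

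*Combined protocol and SAP*

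**What the plan says.** **Recruitment.** Section 8.3 states the aim: "To reduce confounding age and pubertal stage, we will use a stratified recruitment method". Three parent questions sort children, so that "children will be initially categorized into Pre/Early and Mid/Late Puberty", and enrolment closes cell by cell. Section 5.2 says of the target child that "this is the youth we select to balance pubertal stage and age". Neither section gives age bands or a balancing method. Targets are 11 to 14 years old (8.1).

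**Measurement.** The stage measure in 5.2 is a youth questionnaire, "which allows placement in Tanner stages for hair, testicles, and breast development". It is a different instrument from the parent screen.

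**Randomisation.** In 14.1, "participants will first be placed into one of four groups based on sex and pubertal stage", and condition is assigned within those groups. The same paragraph then says: "Pubertal stage will then be treated as a continuous variable".

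**Analysis.** Section 14.3 first tests condition x sex x pubertal stage for cortisol and alpha-amylase AUCi, then two-way terms, then main effects. Covariates are chosen by association: "Those covariates that are associated with the independent and outcome variables will be controlled for in the primary analyses". Section 14.2 calls the three-way model "the most complex model considered in our primary analysis, see equation 1 below". Neither that equation nor the covariate list in the cited section 4.3 is in the text available for this review. The prose mentions no age interaction.

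**The concern.** Condition is randomised; pubertal stage is observed. A condition x puberty interaction shows that the condition effect differs along the puberty scale, but not that puberty is the reason. Age is the obvious rival. Section 2.3 reports that parental buffering was absent both in 15- and 16-year-olds and in 11- to 14-year-olds at more advanced stages.

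The design addresses this through recruitment balance alone, and that balance is set on two coarse cells while the model uses a continuous score. If age and stage still move together inside a cell, age-driven moderation passes into the puberty term. Entering age as a covariate does not stop this: a main effect is one slope common to all conditions, and the rival explanation is a slope that differs by condition.

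At stake is the label put on the moderation. Puberty is in the stated purpose (1.1), in the first term tested (14.3) and in the exploratory secondary outcome (3.2). As described, the analysis would not show whether the effort to separate age from puberty had worked.

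**Working it through.** **1. The plan's own figure.** Section 14.2 gives a minimum detectable f² of 0.056 (n = 200, alpha 0.05, power 0.80, 12 covariates). It is used here only as a scale.
- Four conditions give u = 3, and lambda = f²(u + v + 1).
- The design terms number 5 main, 7 two-way and 3 three-way, so 15. Then v = 200 - 1 - 12 - 15 = 172, which gives 0.063.
- Of the variants tried, only u = 3 with v = n - 4 returns both 0.056 and the 0.070 stated for n = 160 (0.0556 and 0.0699).
- That is a separate matter, and nothing below depends on it.

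**2. What the missing term does.** Suppose the condition effect changes by d per SD of age and not at all with puberty. If standardised age and stage correlate at r, the fitted condition x puberty slope averages r x d. The chance of a significant puberty interaction follows from

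lambda = (u + v + 1) x f²r² / [1 + f²(1 - r²)].

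Take f² = 0.056, r = 0.5, u = 3 and v = 200 - 1 - 11 - 15 = 173 (11 covariates other than age). Then lambda = 177 x 0.014 / 1.042 = 2.38, and the rejection rate at 0.05 is 22%.

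**3. What balancing leaves.** The documents give neither r nor an age effect; r = 0.3, 0.5 and 0.7 are assumptions. The simulation used n = 200, 50 per sex x puberty cell, ages uniform from 11 to 15, stage split at its median, 11 noise covariates, and 6,000 trials per setting (Monte Carlo SE at most 0.7 points). Balancing means equal numbers per age half, or per year of age, within each cell.

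| | r = 0.3 | r = 0.5 | r = 0.7 |
|---|---|---|---|
| Remaining r, halves balanced | 0.16 | 0.29 | 0.47 |
| Remaining r, years balanced | 0.13 | 0.22 | 0.36 |

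False condition x puberty rejections at 0.05, with age-only moderation:

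| | r = 0.3 | r = 0.5 | r = 0.7 |
|---|---|---|---|
| f² = 0.056, years balanced | 5% | 8% | 12% |
| f² = 0.056, halves balanced | 6% | 10% | 17% |
| f² = 0.056, unbalanced | 11% | 21% | 41% |
| same, age main effect added | 11% | 22% | 41% |
| same, age, condition x age and sex x age added | 5% | 5% | 5% |
| f² = 0.02, halves balanced | 6% | 6% | 8% |
| f² = 0.02, unbalanced | 7% | 10% | 17% |

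Checks:
- The formula in step 2, with the remaining r put in, gives 6%, 8%, 13% (years), 6%, 10%, 20% (halves) and 10%, 22%, 41% (unbalanced).
- A second simulation at f² = 0.056 gave 5%, 7%, 12%; 5%, 11%, 19%; and 12%, 21%, 39%.
- The three-way term behaves alike: 10%, 22%, 41% unbalanced, and 5 to 6% with the full age terms.

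**4. Why the continuous score matters.** In a separate run with the two cells matched on age, age correlated 0.00 with the binary cell but 0.11, 0.18 and 0.25 with continuous stage. With a condition x age effect of 0.4 SD per SD of age, the false puberty slope was 0.04, 0.05 and 0.06, about 11 to 15% of the age effect, and rejections stayed at 5 to 6%. With the binary cell as the analysis variable, the false slope was about zero.

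**The case against.** The case on the other side is strong, and much of it stands.

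- **The plan intends balance, and under balance the effect is small.** This stands. Someone who looks only at the unbalanced rows might infer that a puberty finding carries a 20 to 40% false-positive risk. The documents do not support that: those rates need balance to fail, r of 0.5 to 0.7, and purely age-driven moderation as large as the plan's detectable effect.
- **A Tanner score has few levels, so less age information remains inside a cell.** This also stands. With an assumed five-level score at f² = 0.056, rejections fall to 6%, 6%, 9% (years balanced) and 6%, 8%, 15% (halves balanced).
- **The recruitment cells may already involve age.** One might infer that only puberty and sex define them. Section 8.3 does not mention sex and does not list the cells exhaustively; age-by-puberty cells would fit its stated aim. The sex x puberty groups in 14.1 concern randomisation.
- **The full model is not visible.** One might also infer that age is certainly left out. Equation 1 and the covariate list could not be seen, so only the prose can be judged. That prose describes covariates, lower-order terms and the three-way term, with no age interaction.
- **Multiplicity correction lowers the rates.** True. In the unbalanced case they are 6%, 14%, 30% at 0.025, and 2%, 5%, 15% at 0.05/9.
- **A sensitivity model cannot settle the cause.** Correct, and the reason to use it for interpretation only. It still shows whether the puberty estimate depends on ignoring age.

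What remains is that the plan neither secures the balance in a stated way nor says it will be reported, so which case applies cannot be known.

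**Conclusion.** The point holds as a gap in attribution. The analysis as described cannot separate puberty-driven from age-driven moderation, and balancing age across two cells does not fully do so when stage enters as continuous. At f² = 0.056 and assumed r of 0.3 to 0.7, false condition x puberty rejections are about 5 to 12% with years balanced, 5 to 19% with halves balanced (both lower for a five-level score), and about 10 to 40% only if balance is not achieved. The sizes rest on the assumed correlation, the assumed age effect and purely age-driven moderation; none of these comes from the documents.

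A reader might go further and infer that the condition comparisons are biased. They are not: randomisation protects every condition contrast, including those within late-puberty youth. The issue is worth correcting because the remedy is cheap and the puberty claim is one the trial intends to make.

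**What to change.** Keep recruitment, randomisation and the primary models as they are. Add to section 14:

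1. Report the achieved correlation between age and analysed pubertal stage, overall and by recruitment cell.
2. Prespecify one sensitivity model per outcome adding age, condition x age and sex x age, plus condition x sex x age when the three-way term is tested. Use age at participation, which 5.4 already provides for, recorded finely enough (for example in months) before birth dates are deleted.
3. Show the puberty interaction estimate and confidence interval from both models before attributing moderation to puberty rather than age. This informs interpretation; it is neither a gate nor an automatic relabelling rule.
4. State the age bands or method used to balance age.

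**Cost.** No new data are needed.
- *Degrees of freedom.* Adding all eight age terms moves the detectable three-way f² from 0.0634 to 0.0665.
- *Precision.* Standard errors grow by 1/sqrt(1 - r²): about 1%, 5% and 13% with halves balanced (r = 0.16, 0.29, 0.47), and about 5%, 15% and 40% unbalanced (r = 0.3, 0.5, 0.7). In the unbalanced case, power for a true condition x puberty effect of f² = 0.056 falls from about 75% to 69%, 60% and 43%.
- *Measurement error.* At an assumed questionnaire reliability of 0.8, a purely pubertal effect shrinks by about 3%, 9% and 23% after adjustment (unbalanced). A smaller adjusted estimate is therefore not proof that age is the cause, and the SAP should say so.

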9.0 Vulnerable Populations

9.1 Vulnerable Populations:

Population / Group	Identify whether any of the following populations will be targeted, included (not necessarily targeted) or excluded from participation in the study.
Children	Targeted Population
Pregnant women/fetuses/neonates	Excluded from Participation

PROTOCOL TITLE: Does Social Buffering Continue to be Effective Over the Peripubertal Period
When Friends Share the Stressor Experience?

VERSION DATE: v.3.3 3.31.23

Prisoners	Excluded from Participation
Adults lacking capacity to consent and/or adults with diminished capacity to consent, including, but not limited to, those with acute medical conditions, psychiatric disorders, neurologic disorders, developmental disorders, and behavioral disorders	Excluded from Participation
Non-English speakers	Excluded from Participation
Those unable to read (illiterate)	Excluded from Participation
Employees of the researcher	Excluded from Participation
Students of the researcher	Excluded from Participation
Undervalued or disenfranchised social group	Included/Allowed to Participate
Active members of the military (service members), DoD personnel (including civilian employees)	Included/Allowed to Participate
Individual or group that is approached for participation in research during a stressful situation such as emergency room setting, childbirth (labor), etc.	Excluded from Participation
Individual or group that is disadvantaged in the distribution of social goods and services such as income, housing, or healthcare.	Included/Allowed to Participate
Individual or group with a serious health condition for which there are no satisfactory standard treatments.	Excluded from Participation
Individual or group with a fear of negative consequences for not participating in the research (e.g.	Included/Allowed to Participate

PROTOCOL TITLE: Does Social Buffering Continue to be Effective Over the Peripubertal Period
When Friends Share the Stressor Experience?

VERSION DATE: v.3.3 3.31.23

institutionalization, deportation, disclosure of stigmatizing behavior).	
Any other circumstance/dynamic that could increase vulnerability to coercion or exploitation that might influence consent to research or decision to continue in research.	Excluded from Participation

9.2 Additional Safeguards:

Children are the targeted population for this study. Others that have been checked as “allowed” above are not being intentionally included or excluded. For example, we will not inquire about someone’s membership in a disenfranchised group. Our careful consent/assent procedures designed to handle research with children should be sufficient to cover other vulnerable participants who may inadvertently enter our study.

All of the subjects will be children, ranging 11-14 years old. This study focuses on adolescents because its goal is an analysis of the impact of social buffering and puberty on stress-mediating systems. Children have been the focus of my research for the past 30+ years. My staff is highly trained in working with children and families. The graduate students working on the project will be Child Psychology and/or Child Clinical Psychology Ph.D. students. The undergraduate research assistants will, for the most part, be majoring in child development.

Our recent experience conducting a study using an online version of the TSST (Zoom/REDCap) with youth aged 14-16) was very positive and well received.

The risks of this study are generally minimal. For the youth, they largely include embarrassment while completing the puberty questionnaires and distress/anxiety during the public speaking task. Youth may experience concern when completing questionnaires dealing with emotional problem symptoms. Parents may experience concern when completing interviews about youth psychiatric symptoms. Any time you work with youth there is the possibility that they will reveal information about abuse and/or indicate that they are thinking of hurting themselves or others. We are mandated reporters, a fact that is revealed in both consent and assent forms. Parents provide consent, youth provide assent, and see below where that process is fully described to ensure that youth have full understanding and are free to decline.

10.0 Local Number of Participants

PROTOCOL TITLE: Does Social Buffering Continue to be Effective Over the Peripubertal Period
When Friends Share the Stressor Experience?

VERSION DATE: v.3.3 3.31.23

10.1 Local Number of Participants to be Consented: We plan to analyze at least 200 target participants. Of those 50 will participate alone, while 150 will participate with a social peer. Social peers will be enrolled as they will at least complete a questionnaire. Thus, we will enroll at least 350 children. To account for attrition between sessions/replacement for incomplete data, we anticipate up to 400 children may be enrolled.

11.0 Local Recruitment Methods

11.1 Recruitment Process: Families will be contacted by phone or email and the procedures will be described. If the family is interested, the first online visit will be scheduled. Copies of the consent and assent forms will be sent to families prior to the visit, along with directions to the University, and a reminder call will be a chance for families to confirm their interest in participation after having seen the consent forms. The formal consent process will occur at the first visit .

Regarding recruitment of the social peer to the target, when that peer is a friend: The family of the participant will contact the family of the friend make sure that they have permission to give us their contact information. Parents of friends who participate will then be emailed a REDCap link to a consent formthat they can complete and sign online before the session.If they do not respond to email in 3 days, our recruiter will call them for a reminder. There will be phone and email contact information so that parents can ask any questions they have before their child comes to theonline. In the event that we are unable to obtain consent for the friend prior to the online session, that session will be converted to the “alone” condition. If we have parental consent for the friend, but not assent by the time of the online session, the assent form will be provided to the friend at session 2, and will also have a line that the parent of the primary participant can sign as a witness to the consent process. We have successfully used this method in the past.

11.2 Identification of Potential Participants: Potential participants will be identified using the ICD registries of families interested in being contacted about research. Those families have agreed to be contacted, and once ICD Registry procedures have been followed, including proof of IRB approval, an encrypted list is provided to study staff. No protected records are involved. Study staff will make initial contact. In our 3/31/23 revision, we use social media (eg., Facebook, Twitter, Instagram) and list serves (eg., ICD or CEHD list serve) to share contents of the approved 11.12.21 recruitment flyer. We would share that flyer, only modified for format. We wish to increase the pool of potential partcipants. For social media posts, commenting will be disabled, to prevent sharing of personal information or inappropriate comments.

PROTOCOL TITLE: Does Social Buffering Continue to be Effective Over the Peripubertal Period
When Friends Share the Stressor Experience?

VERSION DATE: v.3.3 3.31.23

11.3 Recruitment Materials: We will recruit via telephone and email (as parents have given us both means of contacting them). We will also post flyers and put the flyer information on our website so that families can contact us. Materials are uploaded in ETHOS.

11.4 Payment: In the four conditions, as follows:

1. No Social Support: We would give the child up to \$50 and parent up to \$20 in debit cards for participating.
2. Unfamiliar Peers Both Tested: For each of the two participants: We would give the child up to \$50 and parent up to \$20 in debit cards for participating.
3. Close Friend Gives Support: We would give the child up to \$50 and parent up to \$20 in debit cards for participating. We would give the friend \$20 debit card for attending, as well.
4. Close Friends Both Tested: For each of the two participants: We would give the child up to \$50 and parent up to \$20 in debit cards for participating.

We intend to use the prepaid debit cards: Greenphire ClinCard for compensation, and have included appropriate language in the consent document. (We will provide a Target gift card instead of the ClinCard if parents object to the terms and conditions of the ClinCard, tho in our experience, this is very rare.) Families will be mailed empty cards, which will be loaded following receipt of the card and completion of the sessions.

11.5 Withdrawal Circumstances: If participants are enrolled (consent signed) and subsequently determined to meet exclusion criteria, their data will be excluded from analyses.

11.6 Withdrawal Procedures: If they have a remaining session scheduled, we will cancel the session. If, however, cancelling will bring undue embarrassment to the child, in consultation with the parent, we will allow the second session to occur. Participants will not be contacted if their participation is complete.

11.7 Termination Procedures: Data will not be used after termination.

